10.1. Efficacy Assessments

10.1.1. Mid-nasal Swab

Participants will collect daily mid-nasal swabs for on Days 1 to 14, 21, and 28 for viral detection.

Participants will receive a swab kit either via courier or mail, which includes a study instruction booklet, swabs, plastic tubes for swab collection, a return box with affixed Category B UN3373 label, as required by IATA guidelines ([UN3373 Medical Packaging 2020](#)), and a pre-paid return shipping label. Participants are instructed to place their self-collected nasal swabs directly into the plastic tube that is pre-labeled with a unique barcode. Next, participants are instructed to place the plastic tube containing the self-collected nasal swab into a specimen bag, pre-packaged with an absorbent sheet, and then place the specimen bag into the provided return shipping box or pouch. Swab kits may contain either viral transport media, 0.9% saline, or phosphate-buffered saline, which have been shown to be equivalent for storage of SARS-CoV-2 samples based on validated assays ([Rodino 2020](#)). Previous testing has demonstrated that respiratory viral RNA is stable in room temperature for up to 1 week.

The used swabs will be collected by the courier or returned via the postal service or shipping service, such as FedEx.

Swabs will be subjected to RNA amplification and tested for SARS-CoV-2.

10.1.2. Participant Survey

Participants will be asked to complete surveys (Daily Surveys and Exit Contact Survey) that will include questions about symptoms from both the drug regimen and respiratory and systemic

symptom, review of concomitant medications, and other pertinent topics. A modified self-reported Flu-Pro instrument will be completed each day through Day 14 and on Day 21 and Day 28 to assess degree of illness (Yu 2020) (Appendix 12).

10.2. *Adverse Events*

Participants will be asked to complete surveys (Daily Surveys and Exit Contact Survey) that include information on any symptoms that they are experiencing. In addition, AE review by a staff member (via telephone, Telehealth, or text messaging) will be performed.

All AEs must be recorded on the electronic case report forms (eCRFs) if any of the following criteria have been met:

- All AEs meeting SAE definition
- All AEs leading to discontinuation of study medication
- All AEs judged by the site Investigator to be associated with study medication

10.2.1. *Adverse Events*

An AE is any untoward medical occurrence that occurs in a patient or clinical investigation subject administered a pharmaceutical product, which does not necessarily have to have a causal relationship with this treatment. An AE can therefore be any unfavorable and unintended sign (including abnormal laboratory findings), symptom, or disease temporally associated with the use of an investigational product, whether or not considered related to the product.

AEs may include the onset of new illness and the exacerbation of pre-existing medical conditions. An AE can include an undesirable medical condition occurring at any time, including baseline or washout periods, even if no study treatment has been administered.

10.2.2. *Serious Adverse Events*

An SAE is defined as any untoward medical occurrence that:

- Results in death
- Is life-threatening
- Requires inpatient hospitalization or prolongation of existing hospitalization
- Results in persistent or significant disability/incapacity
- Is an important medical event that may not be immediately life-threatening or result in death or hospitalization but may jeopardize the participant or may require intervention to prevent one of the other outcomes listed in the definition above

All AEs that are recorded must have their severity graded. To grade AEs, sites should refer to the DAIDS AE Grading Table, corrected Version 2.1, July 2017, which can be found on the DAIDS Regulatory Support Center website at [https://rsc.tech-res.com/docs/default-source/safety/division-of-aids-\(daids\)-table-for-grading-the-severity-of-adult-and-pediatric-adverse-events-corrected-v-2-1.pdf](https://rsc.tech-res.com/docs/default-source/safety/division-of-aids-(daids)-table-for-grading-the-severity-of-adult-and-pediatric-adverse-events-corrected-v-2-1.pdf).

10.2.3. *Treatment-related AE and SAE*

A treatment-related adverse event is defined as any new AE that begins, or any preexisting condition that worsens in severity, after at least 1 dose of study treatment has been administered until the end of study (i.e., Day 28) and is considered by the Investigator to be related to the study medication.

All AEs and SAEs should have attribution recorded as treatment- or not treatment-related, in the judgment of the site Investigator.

10.3. *Treatment of Overdose*

Overdose of HCQ, azithromycin, or LPV/r should be managed according to the labeling information (see [Appendix 5](#), [Appendix 6](#), and [Appendix 7](#), respectively). Study drug overdose, including misuse or abuse of the product and medication errors, should be reported in the eCRF in the clinician notes.

Ascorbic acid and folic acid exhibit low toxicity; risks from overdose are expected to be minimal.

10.4. *Pregnancy*

Pregnancies occurring in participants enrolled in this study must be reported and followed to outcome. Pregnancy alone is not regarded as an AE unless there is a possibility that the study drug may have interfered with the effectiveness of a contraceptive medication. Elective abortions without complications should not be considered AEs unless they were therapeutic abortions. Hospitalization for normal delivery of a healthy newborn should not be considered an SAE. Pregnancy is not considered an SAE unless there is an associated serious outcome. Spontaneous abortions should always be reported as SAEs.

10.5. *Safety Assessments*

Safety will be assessed via participant Surveys, as shown in the SoA.

Participants will be asked to complete surveys (Daily Surveys and Exit Contact Survey) that include questions about their health, healthcare seeking, symptoms, illness within their household, contact, and mobility. Qualifying events will be recorded on the eCRF and reported as AEs, as described in [Section 10.2](#).

10.6. *Dried Blood Spot Sub-study (Optional)*

All participants will be offered enrollment into the DBS sub-study. For those study sites not wishing to participate in the DBS sub-study, this will not be considered a protocol deviation.

Participants will receive instructions for DBS self-collection in writing, with telephone, Telehealth, and text messaging options as support. Once cards have been dried, they will be collected by the study courier and returned to the laboratory.

The aim of the DBS sub-study is to evaluate HCQ, azithromycin, and LPV/r drug concentrations as an adherence measure and the PK of HCQ, azithromycin, and LPV/r. If serological assays for SARS-CoV-2 are available, DBS may be tested for SARS-CoV-2 antibodies.

Pharmacokinetics

The exposure-response relationship of HCQ, azithromycin, or LPV/r of patients treated for SARS-CoV-2 has not been established. Population PK analyses can be used to further inform dose selection in other populations and support concentration-response investigations with efficacy and safety outcomes.

To accomplish this, sparse PK sampling techniques can be employed. This would involve collection of whole blood at 1 to 5 times after dosing has commenced. The time of collection post-dose can be random.

Given the long half-lives of HCQ and azithromycin, samples for several weeks after the last dose are also informative to the population PK model development.

The basic requirements for PK sampling are as follows:

1. Accurate record of time of the dose prior to the blood sampling (dd:mm:yy; hh:mm)
2. Accurate recording of time of blood sampling (dd:mm:yy; hh:mm) for each blood sampling
3. Whole blood can be obtained by venipuncture or capillary blood by skin puncture using a lancet
4. Approximately 100 μ L of blood is then applied to filter paper as outlined in [Appendix 9](#)

Anti-SARS-CoV-2 Antibody Testing

DBS sample for serology will be collected at Day 28 and tested for SARS-CoV-2 antibodies provided that an appropriate test is available.

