3.2.11. Rationale for Ascorbic Acid Control as a Comparator for HCQ and LPV/r

In healthy adults, COVID-19 disease is likely to present as an upper respiratory viral infection, characterized by a febrile disease with cough and fatigue (Huang 2020; WHO Feb 2020). Symptom reporting may vary based on the participants' perception as to whether they are taking HCQ or ascorbic acid (Barrett 2011), but the primary study endpoints are not affected. There is no rigorously proven therapy for individuals with outpatient COVID-19 disease, although multiple therapies are under investigation.

Because there is no established therapy, use of a control is acceptable and ethical for both the participants' health and safety as well as ensuring the most rigorous trial design to evaluate an intervention for COVID-19 disease caused by SARS-CoV-2. Participants will be blinded to their allocation to the extent possible. However, LPV/r will not appear similar to ascorbic acid. If >1 individual from the same household is enrolled, all will be assigned to the same randomized group.

The dose of ascorbic acid chosen for this protocol is safe. All participants, regardless of assigned group, will be able to take additional ascorbic acid (e.g., over the counter vitamins or through food) should they choose, as there is no known maximum daily safe dose of ascorbic acid. Clinical trial evidence has demonstrated that ascorbic acid, alone or in combination with other micronutrients, does not substantially reduce the risk of upper respiratory infections or severe consequences of infectious processes (Fujii 2020; Graat 2002); thus, ascorbic acid is not expected to have a prevention effect for SARS-CoV-19 and is considered a placebo-equivalent product for this study.

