Gastrointestinal disturbance

Nausea, vomiting, and diarrhea are common known possible side effects of LPV/r. Taking with food may improve tolerability. Participants will be counseled extensively about this risk. Ondansetron 4 mg tabs (#10) as needed for nausea and vomiting and loperamide 2 mg tabs (#10) as needed for diarrhea will be provided to each participant. A small supply will be given to participants for at least 2 days of symptom relief. It is anticipated that if symptoms are not controlled with the available medications, that participants may not be able to tolerate study medication. Loperamide is a well tolerated medication available over the counter. Risks include constipation, abdominal cramps. In rare cases, allergic reaction, fatigue/drowsiness, or toxic megacolon may occur. Up to 16 mg can be used per day. With higher than recommended doses, there is risk of QT prolongation. Participants will be instructed not to take more than 4 tablets (8 mg) of loperamide per day. Those participants who take more than the recommended dosage to control diarrhea will have study medication held to reduce the risk of QT prolongation.

Ondansetron may be associated with headache, fatigue, and malaise. Constipation may also occur. Allergic reaction/hypersensitivity may also occur. Participants will be instructed not to take more than 12 mg per day of ondansetron. Those participants who take more than the recommended dose to control symptoms will have study medication held to reduce the risk of QT prolongation.

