11.3.2.1. Safety Analyses

All safety analyses will be performed on the Intention-to-Treat population. AEs will be compared by study group.

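### Ordinary tolerability AEs are compared by arm, but they enter the data only if the investigator attributes them to study drug: events are lost in both arms, and bias is possible if allocation is guessed

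*Protocol*

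**What the plan says.** Protocol Section 10.2 sets the recording rule: "All AEs must be recorded on the electronic case report forms (eCRFs) if any of the following criteria have been met". The three criteria are "All AEs meeting SAE definition", "All AEs leading to discontinuation of study medication" and "All AEs judged by the site Investigator to be associated with study medication". The first two need no causal judgement. Any other AE has only the third route. Section 10.5 confirms that only qualifying survey events become AEs on the eCRF.

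Section 11.3.2.1 states: "AEs will be compared by study group". It names the ITT population but no method, and it does not limit which AEs are meant. The secondary safety endpoint in Section 4 is narrower: SAEs and AEs that lead to stopping treatment.

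On expected effects, Section 7.4 says of the active arm: "Nausea, vomiting, and diarrhea are common known possible side effects of LPV/r". Section 10.3 says of the comparators: "Ascorbic acid and folic acid exhibit low toxicity; risks from overdose are expected to be minimal".

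On masking, Section 3.2.11 says: "However, LPV/r will not appear similar to ascorbic acid". Section 7.6.1 says that participants and treating clinicians are blinded and that study clinicians do not see the medication.

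The SAP introduction limits that document to the three arms first implemented, so it gives no safety analysis for LPV/r.

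**The concern.** Section 10.2.1 defines an AE regardless of cause, but the recording rule in Section 10.2 keeps a non-serious, non-discontinuing event only when a cause has been assigned. The by-arm comparison of such events therefore measures incidence multiplied by the probability of attribution.

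This matters most for gastrointestinal events. They are the expected toxicity of LPV/r, and nausea, stomach ache, vomiting and diarrhoea are also items on the modified Flu-PRO (Appendix 12), so attributing them is a judgement call. Two things are at stake. Real events are missing from both arms, which weakens the tolerability comparison. And if investigators form a view of the allocation, the same symptom could be recorded in one arm and left out in the other.

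**Working it through.** **Which events are filtered.**

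| Event | Needs attribution to reach the eCRF? | In the named safety endpoint? |
|---|---|---|
| SAE | No | Yes |
| AE leading to discontinuation | No | Yes |
| Any other AE | Yes | No, but within the unrestricted AE comparison of Section 11.3.2.1 |

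Section 10.2.3 asks for attribution to be recorded for all AEs and SAEs. That does not contradict the filter, because an SAE or a discontinuation AE can be on the eCRF and be unrelated.

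**Inputs.** The plan gives no AE rate, attribution rate or safety power, so there is no figure of its own to reproduce. From the documents: 173 per arm (Section 11.1.1), 1:1 allocation. Assumed: true incidence p, and attribution probabilities q1 (LPV/r) and q0 (ascorbic acid). Recorded rates are then p × q1 and p × q0. Rejection probabilities are for a two-sided 5% pooled z-test, by exact binomial enumeration. The plan names no test, and household clustering is ignored, so these figures are illustrations.

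**Blind intact (q1 = q0).**

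- There is no bias. With p = 20% in both arms and q = 0.5, 173 × 0.20 = 34.6 participants per arm have the symptom and 17.3 per arm are recorded. The chance of a spurious LPV/r excess is 2.6%, against a nominal 2.5%.
- Information is lost. For an assumed true difference of 40% vs 25% and q = 0.45, recorded rates are 0.40 × 0.45 = 18% and 0.25 × 0.45 = 11.25%. The ratio stays at 1.6, but the difference shrinks from 15 to 6.75 percentage points and power falls from 85% to 43%.

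**Attribution differs by arm, equal true incidence.** With q1/q0 = 0.6/0.4 the recorded rate ratio is 1.5, and the chance of a spurious significant LPV/r excess is 13%, 24% and 35% for p = 10%, 20% and 30%. With 0.7/0.3 the ratio is 2.3, and the chances are 40%, 72% and 89%.

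**How guessing drives this.** Suppose attribution is 0.7 when LPV/r is believed, 0.2 when ascorbic acid is believed and 0.45 with no belief. Let a fraction c guess correctly and w wrongly. Then

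q1 = 0.7c + 0.2w + 0.45(1 − c − w), q0 = 0.2c + 0.7w + 0.45(1 − c − w), so q1 − q0 = 0.5(c − w).

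| c | w | Recorded at p = 30%, LPV/r vs control | Chance of a significant difference, p = 30% | Range for p = 20-40% |
|---|---|---|---|---|
| 0 | 0 | 13.5% vs 13.5% | 5% | 5% |
| 0.3 | 0 | 15.75% vs 11.25% | 23% | 17-31% |
| 0.3 | 0.2 | 14.25% vs 12.75% | 7% | 6-8% |
| 0.6 | 0 | 18% vs 9% | 70% | 51-84% |
| 0.6 | 0.4 | 15% vs 12% | 13% | 10-16% |

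What matters is the excess of correct over wrong guesses. Assuming that no guess is wrong gives the large figures; allowing wrong guesses removes most of the effect.

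**Can the attributing investigator learn the arm?** Tablet number does not reveal it. Section 7.1 lists 200 mg-50 mg LPV/r tablets and 250 mg ascorbic acid tablets. Day 1 doses are 800/200 = 4 and 1000/250 = 4 tablets; later doses are 400/200 = 2 and 500/250 = 2. Ondansetron and loperamide go to every participant (Section 7.4). The remaining route is through the participant, who sees the tablets, is counselled on LPV/r gastrointestinal effects (Section 7.4), speaks with study staff by video or telephone (Section 9.3) and is asked about medication at each contact (Section 7.9).

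**The case against.** The strongest reply is that the attributing investigator does not see the tablets, the counts match, and the named safety endpoint bypasses the filter. Section 11.3.2.1 sits under the secondary endpoints, so its AE sentence can be read as meaning that endpoint. For the earlier arms, SAP Section 6.2 plans frequency tables of SAEs, discontinuation AEs and cardiac versus non-cardiac events, with no significance test. Selective AE recording for a drug with a long safety record is also a legitimate design choice.

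Most of this stands. A reader might infer that COVID-19 nausea or diarrhoea will in fact be recorded more often on LPV/r because the tablets look different. The documents do not support that: it needs a further step, disclosure or a guess, which Section 7.6.1 is meant to prevent. The Introduction claims only partial masking, so the step is possible, but it is not shown.

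A reader might also infer that intolerance will be hidden because Section 8.1 lists a participant's request separately from an AE as a reason to stop. That is conjecture. The second recording criterion covers an AE leading to discontinuation whoever asks to stop, and the Grade 1 or 2 paragraph in Section 7.4 concerns toxicity already judged related, which the third criterion captures.

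What the reply does not remove is the loss of unattributed events, which occurs under perfect masking, or the unrestricted wording of Section 11.3.2.1, which no LPV/r analysis plan clarifies.

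**Conclusion.** The point holds in a limited form. For non-serious, non-discontinuing AEs, the by-arm comparison is attribution-filtered. The loss of unattributed events follows from Section 10.2 whenever some events are not attributed; how many are lost is unknown, because no attribution rate is given. Differential recording is a risk that depends on the blind failing. Its size cannot be derived from the documents: under the assumptions above, the chance of a spurious difference runs from the nominal 5% to 84%, and the upper end requires that nobody guesses wrongly. These figures show sensitivity and do not estimate what will happen. The SAE and discontinuation endpoint is not attribution-filtered and is not called into question.

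**What to change.** In Section 11.3.2.1:

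1. State that the formal by-arm AE comparison is of SAEs and AEs leading to discontinuation, as in Section 4. Present other investigator-attributed AEs as descriptive only.
2. Add a by-arm comparison of the proportion of participants with nausea, vomiting, stomach ache or diarrhoea rated *somewhat* or higher on the modified Flu-PRO on Days 2-14, and of the number of days with such symptoms. SAP Section 4.1.1 uses the same threshold for cough and dyspnoea, and SAP Section 7.2 already leaves out Day 1.
3. Add a by-arm comparison of permanent study-drug discontinuation for any reason, tabulated by the reason recorded under Section 8.1. This avoids relying on how a stop is classified; hospitalization is one of the listed reasons, so the breakdown is needed.

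Account for household clustering in items 2 and 3, as Section 11.3.1 does for efficacy.

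The cost is wording and a small amount of extra tabulation from data already collected; no study procedure changes. There are two downsides. Solicited gastrointestinal items include illness symptoms in both arms, which dilutes a drug effect. And self-report comes from the people who see the tablets, so it can still be influenced by perceived allocation, as Section 3.2.11 concedes for HCQ. For that reason these comparisons should supplement the SAE and discontinuation analysis and not replace it.

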10.7. Biohazard Containment

As the transmission of SARS-CoV-2 and other respiratory droplet pathogens can occur through contact with respiratory droplets and contaminated surfaces, precautions will be employed by all personnel in the handling of all specimens for this study, as currently recommended by the Centers for Disease Control and Prevention and the National Institutes of Health.

All dangerous goods and materials, including diagnostic specimens and infectious substances, must be transported using packaging mandated by Code of Federal Regulations 42 Part 72. Please refer to instructions detailed in the IATA Dangerous Goods Regulations.

11. Statistical Considerations

11.1. Sample Size Determination

The overall size of the study is driven by the clinical endpoint, resolution of COVID-19 symptoms.

11.1.1. COVID-19 Endpoints

Overall sample size will depend on the number of events observed. To detect at least a 1.5-fold increased risk of the COVID-19 symptom resolution rate under a null hypothesis of no reduction

and four interim monitoring analyses with stopping for futility and efficacy based on the O'Brien-Fleming bounds and 80% power, the trial is designed to achieve 99 events per pairwise comparison for the symptom resolution endpoints. To achieve this, 173 participants will be enrolled per arm.

As the initial sample size target, 210 per arm was chosen for each experimental group (HCQ, HCQ + azithromycin), assuming a control arm rate of approximately 30% and 5% dropout rate.

HR (active/control)	Events/arm	N per arm	Median control arm (days)	Median active arm (days)*
1.4	142	247	10	7
1.5	99	173	10	7
1.6	75	129	10	6
1.7	59	103	10	6
1.8	49	85	10	6
1.9	41	71	10	5
2,0	36	63	10	5

*Under constant baseline hazard assumption

11.1.2. *Viral Shedding Endpoint*

Assuming the median time to cessation of viral shedding is 10 days and a constant baseline hazard for cessation of shedding, approximately 62% of participants would no longer experience viral shedding at 14 days under the null hypothesis of no intervention effect. Assuming 420 participants per pairwise comparison, 90% statistical power, 1-sided type I error rate of 2.5% for efficacy, we can detect at least a 37% increase in the rate of cessation of viral shedding. Under an extreme example of having only half that sample, 210, we could detect an increase of 54% or higher.

11.2. *Populations for Analyses*

For analysis purposes, the following populations are defined and will be described in greater detail in the trial Statistical Analysis Plan:

Population	Description
Intention to Treat (ITT)	All enrolled participants
Modified ITT	All enrolled participants who do not have LRTI at Baseline: high-risk group for the primary clinical endpoint; high- and low-risk groups (separately) for the primary virologic endpoint.
PK evaluable	Participants from the DBS sub-study with at least 1 interpretable PK sample.

DBS: dried blood spot; PK: pharmacokinetic; PCR: polymerase chain reaction; SARS-CoV-2: severe acute respiratory syndrome coronavirus 2.

11.3. *Statistical Analyses*

The Statistical Analysis Plan will be developed and finalized before database lock and will describe the participant populations to be included in the analyses, the detailed analytical plans with endpoints and procedures for accounting for missing, unused, and spurious data. An Interim Monitoring Plan will also be developed to describe approaches for re-estimation of sample size and any planned interim analyses. This section presents a brief summary of the planned statistical analyses of the primary and secondary endpoints (these are listed in [Section 4](#)).

11.3.1. *Efficacy Analyses*

Demographic characteristics (age, sex, race) of each study group will be tabulated.

The mean age (plus range and standard deviation) by sex of the enrolled participants, as a whole and per group, will be calculated.

Primary analyses: The primary analyses will be conducted on the intend-to-treat population overall and by cohort (high-risk and low-risk). Participants randomized to each active treatment will be compared to participants randomized to placebo (ascorbic acid). If appropriate, the primary analysis will make use of all participants randomized to placebo, whether contemporaneously enrolled or not, using an Empirical Bayesian information borrowing method (described below). Due to anticipated heterogeneity in risk of disease progression, pre-specified baseline variables, including age, BMI, and days of symptoms at time of enrollment will be included in the model to increase precision.

Both primary endpoints will be analyzed using a Cox proportional hazards model with robust standard errors, adjusted for within household correlation.

As-treated analysis: The primary analyses will be repeated, replacing randomization arm by actual treatment to account for possible off-label use of and noncompliance to the investigational products.

Subgroup analyses: All subgroup analyses will be pre-specified in the Statistical Analysis Plan. Any further subgroup analyses will be considered ad hoc.

Missing Data

Due to the design of the study and retention activities, measurable outcomes are expected for all participants. However, in the unlikely event of a missing test result, the missing data will be imputed.

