
 To test whether LPV/r is associated with decreased viral shedding from self-collected nasal swabs over 14 days compared to placebo 	
 Proportion of days with SARS-CoV-2 detected from mid-nasal swabs by PCR Median quantity of SARS-CoV-2 detected from mid-nasal swabs by PCR
Exploratory	

 To assess pharmacokinetics and exposure-response relationship of LPV/r 	
 LPV/r blood concentration in DBS

COVID-19: coronavirus disease; DBS: dried blood spot; Flu-PRO: inFLUenza patient-reported outcome; LPV/r: lopinavir-ritonavir; LRTI: lower respiratory tract infection; SARS-CoV-2: severe acute respiratory syndrome coronavirus 2; SpO2: blood oxygen saturation level; WHO: World Health Organization.
	

Sample Size:

The study will enroll 173 participants per arm to achieve 80% statistical power at 2-sided type I error rate of 5% for a pairwise comparison against the control to detect a treatment effect of hazard ratio of 1.5 for the primary outcome(s) assuming control event rate of 60% for the primary outcome and 5% dropout rate. Additional controls will be added to allow for contemporaneous controls for the LPV/r arm. Eligible participants will be randomized at a 1:1 ratio LPV/r + and Ascorbic acid. If a second eligible patient is in the same household, both will be assigned to the same regimen. A blinded sample size re-assessment may be done to possibly increase the target sample size, conditional on the observed incidence rate and within household correlation. Should a new intervention be added, the randomization ratio may be adjusted to favor the new arm, ensuring that control arm participants are still enrolled concurrently with active arms; an empirical Bayesian information borrowing method may be used to incorporate past control arm data for the comparison of new intervention that is added later.

Duration:

Twenty-eight days of clinical follow-up per participant.

Proposed Sites (up to 6): University of Washington, Tulane, Boston University, Cook County, and others to be discussed

2. Schedule of Activities

Procedure	Screening	Self-quarantine									EOS	
		Treatment Period										
	Day 0 ^a	Day 1 ^a	Day 2 ^a	Day 3	Day 4 ^a	Days 5 to 8	Day 9 ^a	Days 10 to 13	Day 14 ^a	Day 21	Day 28 ^b	
Informed consent	X											
Demography	X											
Sign HIPAA form	X											

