1.5.1. LRTI and Hospitalization Endpoints

Overall sample size will depend on the number of events observed. To detect at least 50% treatment efficacy in reducing LRTI or hospitalization/death under a null hypothesis of no reduction, four interim monitoring analyses with stopping for futility and efficacy based on the O'Brien-Fleming bounds and 90% power, the trial is designed to achieve 93 events per pairwise comparison for the LRTI and hospitalization endpoints. For two active arms and one control arm, the total number of events required for each endpoint is 124.

As the initial sample size target, 165 per arm was chosen for each experimental group (HCQ, HCQ + azithromycin), assuming a control arm rate of approximately 30% and 5% dropout rate.

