1.5.2. Viral Shedding Endpoint

Assuming the median time to cessation of viral shedding is 10 days, with a constant baseline hazard for cessation of shedding, 90% statistical power, 1-sided type I error rate of 2.5% for efficacy and early stopping for futility, the design (including interim analyses) can detect 60% or greater increase in the rate of shedding cessation in the combined high- and low-risk cohorts with 200 viral clearance events per pairwise comparison.

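### Protocol 11.1.1 gives 99 symptom-resolution events as the total for the two arms compared, but 99 is the per-arm count; the two-arm total is about 198, and enrolment of 173 per arm stands

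*Protocol*

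**What the plan says.** Protocol Section 11.1.1 says that overall size depends on the events observed. It assumes a 1.5-fold resolution rate, 80% power, and four interim analyses with O'Brien-Fleming stopping for efficacy and futility. It then says "the trial is designed to achieve 99 events per pairwise comparison for the symptom resolution endpoints" and continues: "To achieve this, 173 participants will be enrolled per arm". The table below that text gives, for HR 1.5, 99 in the column headed as events per arm and 173 as N per arm.

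The Synopsis (Sample Size) supplies the other inputs: two-sided 5% type I error, a 60% control event rate and 5% dropout. Section 7.5 gives 1:1 allocation.

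The same unit appears in three other places:

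- Protocol Section 11.1.2: "Assuming 420 participants per pairwise comparison".
- SAP Section 1.5.1: 93 events for each pair of arms, and for two active arms plus control "the total number of events required for each endpoint is 124".
- SAP Section 1.5.2: "200 viral clearance events per pairwise comparison", for a 60% increase at 90% power.

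On monitoring, Protocol Section 11.3 says: "An Interim Monitoring Plan will also be developed to describe approaches for re-estimation of sample size and any planned interim analyses".

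**The concern.** With 1:1 allocation, 99 cannot be both the count in one arm and the count in the two arms together. If the sentence is read as the documents use the phrase elsewhere, the event target is half of what the stated power needs.

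The event target matters because Section 11.1.1 ties study size to events, and Section 5.1 lets the interim decision rest on pooled events. The SAP provided covers only the first three arms, so nothing in it corrects the figure for lopinavir-ritonavir. Whoever writes the Interim Monitoring Plan would find 99 in the running text as the pairwise total. An analysis triggered at that count, or information fractions computed from it, would rest on half the intended information.

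**Working it through.** **Inputs.** HR 1.5, 80% power, two-sided 5%, 60% control event rate, 5% dropout (Synopsis); 1:1 allocation (Protocol 7.5); four interim analyses plus a final one (Protocol 11.1.1). (1.960 + 0.842)² = 7.85.

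**1. Reproduce the table.** Freedman's two-arm total is 7.85 × [(HR + 1)/(HR − 1)]². At HR 1.5 this is 7.85 × 25 = 196.2, or 98.1 per arm. Dividing events per arm by 0.60 × 0.95 = 0.57 gives N per arm.

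| HR | Freedman events per arm | Table events | Freedman per arm / 0.57 | Table N per arm |
|---|---|---|---|---|
| 1.4 | 141.3 | 142 | 247.9 | 247 |
| 1.5 | 98.1 | 99 | 172.1 | 173 |
| 1.6 | 73.7 | 75 | 129.3 | 129 |
| 1.7 | 58.4 | 59 | 102.4 | 103 |
| 1.8 | 48.1 | 49 | 84.3 | 85 |
| 1.9 | 40.7 | 41 | 71.5 | 71 |
| 2.0 | 35.3 | 36 | 62.0 | 63 |

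All seven event counts agree to within about 1.3, and N to within about 1. The table column is per arm, as its header says.

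**2. Test 99 as a two-arm total.** Schoenfeld: 4 × 7.85 / (ln 1.5)² = 191.0. Freedman: 196.2. Even a one-sided 5% test needs 151. No variant tried gives 99. A pair total of 99 would also need only 99 / (2 × 0.57) = 86.8 participants per arm, not 173.

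**3. Events expected from 173 per arm.** Control: 173 × 0.95 × 0.60 = 98.6. Active at HR 1.5: 173 × 0.95 × (1 − 0.4^1.5) = 122.8. The total is 197.2 with no effect and 221.4 at HR 1.5.

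**4. What the phrase means elsewhere.**

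- 420 participants is 2 × 210.
- 93 events split 2:1 at HR 0.5 is 62 control and 31 active; with a second active arm, 62 + 31 + 31 = 124. The two-arm total at 90% power with symmetric O'Brien-Fleming bounds is 92.1.
- For HR 1.6 at 90% power, the same bounds give a two-arm total of 200.3, against the SAP's 200.

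Each is a figure for both arms.

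**5. Power for HR 1.5 by pooled events.** Fixed design: Φ(0.4055 × √D / 2 − 1.96). The group-sequential rows assume five equally spaced analyses and come from 2,000,000 simulated paths. The documents do not specify a futility bound, so the last two rows rest on assumed bounds.

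| Design | D = 99 | D = 198 | D = 221 |
|---|---|---|---|
| Fixed | 52% | 81% | 85% |
| O'Brien-Fleming efficacy only | 51% | 80% | 84% |
| Symmetric O'Brien-Fleming efficacy and futility | 50% | 79% | 84% |
| O'Brien-Fleming-type beta-spending futility | 51% | 77% | 80% |

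With the symmetric bounds the inflation is 1.052, so 191.0 × 1.052 ≈ 201 events are needed for 80%. At 99 pooled events the HR detectable with 80% power is 1.76 (Schoenfeld) to 1.78 (Freedman).

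**Side note, for the record.** SAP 1.5.1 says "As the initial sample size target, 165 per arm was chosen for each experimental group". At a 30% control rate and 5% dropout this gives 165 × 0.95 × (0.30 + 0.15) = 70.5 events per pair, or 165 × 0.95 × (0.30 + 1 − 0.7^0.5) = 72.6, against its target of 93. Those arms had already stopped.

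**The case against.** The strongest reply is that the protocol corrects itself at once. The table carries the right label, the next sentence fixes 173 per arm, and several other sections repeat 173. On this view the slip changes neither sample size, type I error nor analysis. The harm needs a future author to prefer the sentence to the table. Section 5.1 calls an interim analysis only possible, and Appendix 3 expects enrolment to finish before a stopping rule is met. That stands as a limit on the consequence: the 50–52% figure is hypothetical. It does not remove the error, because the sentence that sets the event target remains wrong and no lopinavir-ritonavir monitoring plan in these documents overrides it.

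A second reply is that 173 is shown only to fit a fixed-design table, whereas the sentence claims 80% power with futility stopping. Household clustering is not modelled either. This is fair. At 198 events, power is 77–79% under the two futility bounds tried. At the 221 events expected under HR 1.5 it is 80–84%, which supports keeping 173, but clustering remains unquantified.

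A third is that the documents' usage is not tight enough to rule out loose wording. Section 11.1.2 is itself loose: a 37% increase at 90% power takes about 420 events, whereas 420 participants at 62% clearance give about 260. The two SAP examples are better evidence, although they concern other endpoints and the earlier arms.

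**Conclusion.** The concern holds. The pairwise event target in Protocol 11.1.1 is understated two-fold: 99 is stated, against 191–196 for a fixed design and about 201 with symmetric O'Brien-Fleming efficacy and futility bounds. It is a labelling error in the text; the table and the enrolment of 173 per arm are sound on the Synopsis inputs. The trial as enrolled is not underpowered. The loss of power arises only if 99 pooled events are used as full information or as an analysis trigger. The conclusion that 99 is per arm rests on the documents' own inputs. The group-sequential powers also rest on assumed bounds and equal spacing, with no allowance for household correlation. The sentence should be corrected before the Interim Monitoring Plan is finalised.

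**What to change.** In Protocol 11.1.1, change the target to 99 events per arm (198 per pairwise comparison) and keep 173 per arm. In the Interim Monitoring Plan, compute information fractions and any event-based re-assessment from 198 events over both arms. Confirm power once the futility bound is specified; it is 77–80% at 198 events under the group-sequential bounds tried. For the record, SAP 1.5.1 could keep 93 events and 90% power as its target and note that 165 per arm was not expected to reach it. The cost is one phrase in one protocol sentence, with no additional participants.
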